10.2. Statistical Considerations for the Phase 1 Randomization

10.2.1. Sample Size and Power Analysis for the Primary Objective

The primary objective for Phase 1 is to compare changes from baseline to 12 weeks in the BPI Interference scores between the PCST and Usual Care groups. The null hypothesis is that the change in BPI Interference score is the same in the PCST and Usual Care groups.

Table 10.2 depicts the minimum detectable difference between the PCST and Usual Care groups in the change in BPI Interference score, for a power of 90%, a type 1 error of 5%, an attrition rate of 20%, standard deviations of change of 2 and 3, a total number of participants ranging from 480 – 800 (participant numbers per Clinical Center ranging from 60 to 100), intra-class correlation coefficients of 0 and 0.02, and an interim analysis of one look at 50% information time. Details of the interim analysis are described in **Section 10.2.3**. All calculations are based on two-sample t tests. As one example, if the total sample size is 640, the number of participants per Clinical Center is 80, the ICC is 0 (i.e., no clustering effect), and the standard deviation of the change in BPI Interference score is 2, the BPI Interference score for PCST would need to decrease by at least 0.62 points if the change in BPI Interference score for Usual Care were 0 (**Table 10.2, Row #2**). As another example, again using the parameters in **Table 10.2, Row #2**, the change in the BPI Interference score would need to decrease by 1.02 in the PCST group if the score decreased by 0.40 in the Usual Care group.

Table 10.2. Minimum Detectable Differences between the PCST and Usual Care Groups in the Change from Baseline to Week 12 in the BPI Interference Score

Row	Total N	Clinical Center n	ICC	Minimum Detectable Between-Group Difference in Change in BPI Interference Score ¹	
				If SD = 2	If SD = 3
1	800	100	0	0.56	0.83
2	640	80	0	0.62	0.93
3	480	60	0	0.72	1.08
4	800	80	0.02	0.73	1.10
5	640	80	0.02	0.78	1.17
6	480	60	0.02	0.86	1.29

¹Effect sizes determined for a power of 90%, at a type 1 error of 5%, an attrition rate of 20%, standard deviations of change of 2 and 3, and an interim analysis of one look at 50% information time, using two-sample t tests.

Each of eight Clinical Centers aims to recruit "m" participants. The University of Washington Clinical Center consists of three recruitment sites: University of Washington, Rogosin Institute, and University of New Mexico. The University of Washington and Rogosin will each recruit 43.75% of the Clinical Center's target, and the University of New Mexico will recruit 12.5% of the target. The University of Pittsburgh Clinical Center consists of two recruitment sites: University of Pittsburgh and University of Pennsylvania. The University of Pittsburgh site will recruit two thirds of the Clinical Center's target and the University of Pennsylvania site will recruit one third of the target. The Vanderbilt Clinical Center consists of two recruitment sites: Vanderbilt University Medical Center and West Virginia University. Vanderbilt University Medical Center will recruit two thirds of the

Clinical Center's target, and West Virginia University will recruit one third of the target. The Yale University Clinical Center consists of three recruitment sites in Veterans Affairs Healthcare Systems; each site will recruit one third of the target. Therefore, there are 14 recruitment sites. When clustering at the recruitment site level is considered in the power calculation, the average cluster size per recruitment site per arm is $\bar{m} = 0.571 \times \frac{m}{2} = 0.286m$, and the standard deviation of cluster size is $s_m = 0.313 \times \frac{m}{2} = 0.156m$. This will yield the design effect of $1 + \text{ICC} \times \left[\left\{ \left(\frac{s_m}{\bar{m}} \right)^2 + 1 \right\} \times \bar{m} - 1 \right]$. For example, for $m = 80$ and $\text{ICC} = 0.02$, \bar{m} is 22.88, s_m is 12.48, and the design effect is 1.574. Thus, the sample size per arm in the power calculation is around $139 \left(\frac{80 \times 8}{2} \times \frac{1}{1.574} \times \{1 - 0.2\} \times \frac{1}{1.173} \cong 139 \right)$ after taking into account the design effect (1.574), the attrition rate (0.2) and the inflation factor of the interim analysis (1.173).

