Randomization will be performed at the level of the individual participant using permuted blocks with stratification by enrolling site and by the presence or absence of opioid use using the criteria provided in **Section 5.3** for the Phase 1 randomization. Treatment assignments will not be masked to participants or research team members because of 1) impracticability, and 2) an interest in implementing the interventions as they would be outside of a trial setting. The trial includes a control group that does not receive an active intervention beyond usual clinical care so it is possible to determine whether changes observed in the active treatment groups are the result of the interventions or the result of either increased attention that accompanies trial participation or the natural history of the condition. Bias will be minimized by performing randomization after collection of baseline data, concealing the allocation order, and ascertaining the patient-reported outcomes, including the primary outcome, using standardized, centrally administered questionnaires by research personnel blinded to treatment assignment. Safety and tolerability will be evaluated through ascertainment of specific adverse events of interest and serious adverse events throughout the duration of the trial.

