10.2.1.1. Rationale for the Selected Sample Size

The trial will aim to enroll 640 participants. Based on the minimum detectable differences in changes of BPI Interference scores under a range of assumptions provided in **Table 10.2**, for the primary objective of comparing PCST with Usual Care in Phase 1, this sample size will allow detection of a difference in the change in BPI Interference score of 0.62 if there is no intra-cluster correlation and a standard deviation of change of 2, or 1.17, under the conservative assumptions of an intra-cluster correlation coefficient (ICC) of 0.02 and a standard deviation of change of 3 (which is larger than the SD of change observed in studies of chronic pain in non-ESRD patient populations⁵⁷). Based on a review of the literature, the Initiative on Methods, Measurement, and Pain Assessment in Clinical Trials identified 1 as the minimal clinically important change *for individuals* on the BPI Interference scale.⁵⁷ However, this group also recognized a critical tenet of randomized trials with between group comparisons: "...criteria for clinically important change in individuals cannot be directly applied to the evaluation of clinically important group differences." Determination of the importance of group differences must be established in the broader context of the disease being treated, the currently available treatments, and the overall risk-benefit evaluation of the treatment. Our proposed sample size will allow us to detect a between-group difference *as small as* the ranges listed above. We hypothesize that the actual observed difference will be larger because we are testing an adaptation of an evidence-based intervention that has had moderate effect sizes in other populations and settings.²⁷⁻²⁹

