10.2.2.1. Analyses of the Primary Endpoint for the Phase 1 Randomization

Question 1 (Table 10.1): Does a PCST intervention consisting of weekly, live, coach-led sessions improve outcomes at 12 weeks?

Question 1 addresses the primary trial hypothesis. The primary efficacy endpoint, the change in BPI Interference between baseline and 12 weeks, and will be analyzed using a linear mixed effects model.⁶² The linear mixed effects model will include fixed effects of intervention, time, and interactions between intervention and time, taking into account the repeated measures over time and clustering of recruitment sites via random effects. All repeated measures of the BPI Interference scores at baseline and 12 weeks will be included in the model as the dependent variable. The linear mixed effects model is expressed as

$$y_{ijk} = \beta_0 + \beta_1 X_{ij} + \beta_2 I(T_{ijk} = 12) + \beta_3 X_{ij} I(T_{ijk} = 12) + \gamma^T \mathbf{W}_{ij} + \theta_i + \alpha_{ij} + \varepsilon_{ijk},$$

where y_{ijk} is the BPI Interference score for participant ij ($i = 1, 2, \dots, 14$; $j = 1, 2, \dots, n_i$; n_i is number of participants from recruitment site i) at time point k ($k = 1, 2$), X_{ij} is the binary intervention indicator ($X_{ij} = 1$ if PCST; $X_{ij} = 0$ if Usual Care) for participant ij , T_{ijk} is the study weeks for participant ij at time point k ($T_{ij1} = 0$ and $T_{ij2} = 12$), $I(\cdot)$ is an indicator function returning 1 (0) if the event is true (false), \mathbf{W}_{ij} is a vector of baseline measures, including the stratification factors, for participant ij , β 's and γ are regression parameters for the fixed effects, θ_i and α_{ij} are the regression parameters for the random effects for recruitment site i and participant ij , respectively, and ε_{ijk} is the random error for participant ij at time point k . Model diagnostics will be conducted to examine the assumption of normality. If there are potential violation of the assumptions, transformations of the data beginning with a log transformation will be explored. The primary efficacy estimand is the contrast of PCST and Usual Care for the change at the 12-week time point; i.e., β_3 . Differences in changes, their 95% confidence intervals, and p-values will be presented.

Question 2 (Table 10.1): Does a PCST intervention consisting of weekly, live, coach-led sessions for 12 weeks followed by IVR for 12 weeks improve outcomes at 24 weeks?

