If the interim analysis with two looks at 50% and 75% information time is conducted, the minimum detectable differences depicted in Table 10.2 will be updated by replacing the inflation factor of 1.173 for the interim analysis with one look at 50% information time with the inflation factor of 1.277 for the interim analysis with two looks at 50% and 75% information time. Table 10.5 depicts the minimum detectable difference between the PCST and Usual Care groups in change in BPI Interference from baseline to 12 weeks, for a power of 90%, at a type 1 error of 5%, an attrition rate of 20%, standard deviations of change of 2 and 3, a total number of participants ranging from 480 – 800 (participant numbers per Clinical Center ranging from 60 to 100), intra-class correlation coefficients of 0 and 0.02, and an interim analysis of two looks at 50% and 75% information time.

Table 10.5. Minimum Detectable Differences between the PCST and Usual Care Groups in the Change from Baseline to Week 12 in the BPI Interference

Row	Total N	Clinical Center n	ICC	Minimum Detectable Between-Group Difference in Change in BPI Score ¹	
				If SD = 2	If SD = 3
1	800	100	0	0.58	0.87
2	640	80	0	0.65	0.97
3	480	60	0	0.75	1.13
4	800	100	0.02	0.76	1.14
5	640	80	0.02	0.82	1.22
6	480	60	0.02	0.90	1.35

¹Effect sizes determined for power of 90%, type 1 error of 5%, attrition rate of 20%, standard deviations of change of 2 and 3, and interim analysis of two looks at 50% and 75% information time, using two-sample t tests.

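### The ICC 0.02 rows of Tables 10.2 and 10.5 use a site-by-arm design effect that the stated design and primary model do not have, so the detectable differences are overstated by about 19% to 31%

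*Combined protocol and SAP*

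**What the plan says.** **Sizing (Section 10.2.1).** The calculation concerns change in BPI Interference from baseline to Week 12: "All calculations are based on two-sample t tests". For the ICC 0.02 rows, "When clustering at the recruitment site level is considered in the power calculation, the average cluster size per recruitment site per arm is" 0.286m, with standard deviation 0.156m. The worked example has m = 80, a design effect of 1.574 and about 139 per arm after 20% attrition and the interim inflation factor of 1.173. Section 10.2.3 builds the two-look table (Table 10.5) in the same way, by "replacing the inflation factor of 1.173 for the interim analysis with one look at 50% information time with the inflation factor of 1.277".

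**Design (Section 4.1).** "Randomization will be performed at the level of the individual participant using permuted blocks with stratification by enrolling site". Every site therefore contributes to both arms.

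**Primary model (Section 10.2.2.1).** Theta_i and alpha_ij "are the regression parameters for the random effects for recruitment site" i and participant ij. There is no site-by-arm or site-by-time term. "The primary efficacy estimand is the contrast of PCST and Usual Care for the change at the 12-week time point", which is beta_3.

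**Rationale for N (Section 10.2.1.1).** With 640 participants the detectable difference runs from 0.62 (ICC 0, SD 2) to 1.17, the latter "under the conservative assumptions of an intra-cluster correlation coefficient (ICC) of 0.02" and an SD of 3. The same section reports that a consensus group "identified 1 as the minimal clinically important change" for an individual, and warns that this threshold does not carry over directly to group differences.

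**The concern.** A design effect built on site-by-arm cells treats the PCST and Usual Care participants of one site as unrelated clusters, much as if sites had been allocated to arms. When participants are randomised within site, a site effect shared by both arms is removed by the comparison and does not inflate its variance. If so, half the rows of both tables give detectable differences and a 90% power that belong to another design. One of those figures, 1.17, is the upper end of the range used to justify 640 participants. The plan calls the ICC and SD values conservative, but does not say that the clustering formula adds a margin of its own.

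**Working it through.** **Inputs.** From Section 10.2.1: power 90%, type 1 error 5%, attrition 20%, SD of change 2 or 3, m = N/8, 14 recruitment sites, mean cell size 0.286m, SD of cell size 0.156m, inflation 1.173 (one look). From Section 10.2.3: inflation 1.277 (two looks). Tests are two-sided (Section 10.2.2). The worked example implies 1:1 allocation.

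**Formulas.**
- Design effect: DE = 1 + ICC × [((s/m̄)² + 1) × m̄ − 1]
- Effective n per arm = (N/2) × 0.8 / inflation / DE
- The detectable difference solves the two-sample t test (noncentral t). It is close to SD × (1.96 + 1.2816) × √(2/n).

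**Step 1: reproduce the plan.** For m = 80, m̄ = 22.88 and (0.156/0.286)² + 1 = 1.2975. So DE = 1 + 0.02 × (1.2975 × 22.88 − 1) = 1.574, and n = 320 × 0.8 / 1.173 / 1.574 = 138.7. The detectable differences are 0.781 (SD 2) and 1.172 (SD 3), against 0.78 and 1.17 printed. The other ICC 0.02 rows also reproduce to rounding.

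**Step 2: what the model implies.** Subtract a participant's baseline score from the Week 12 score in the Section 10.2.2.1 model:

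y_ij2 − y_ij1 = β₂ + β₃X_ij + (ε_ij2 − ε_ij1)

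The site intercept θ_i, the participant intercept and the baseline covariates all drop out, so the site variance cannot enter the variance of the β₃ estimate. Suppose instead that the ICC refers to change, with a site effect u_i shared by both arms. The arm contrast then contains Σ(w_i1 − w_i0)u_i, where w is each arm's share of participants from site i. Randomisation stratified by site makes the two shares nearly equal, and the term vanishes again. Only separate, independent effects for each site-arm cell survive.

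**Step 3: check by simulation.**
- Model of Section 10.2.2.1, with the plan's 14 site shares, 257 completers per arm, SD of change 2 and 20,000 replicates. The participant-intercept variance of 3 is an assumption, and it cancels. With a score ICC of 0, 0.02 and 0.10, the variance of the change contrast relative to no clustering is 1.00, 1.02 and 0.99 (Monte Carlo SE 0.01).
- Site effect on change shared by both arms, ICC 0.02, 4,000 replicates: ratio 0.97 to 1.02 over N = 480 to 800.
- Independent effects for each site-arm cell, ICC 0.02, 4,000 replicates: ratio 1.35, 1.42 and 1.55 for N = 480, 640 and 800. Only this case inflates the variance.

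**Step 4: recompute with DE = 1.** Differences are given as SD 2 / SD 3.

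| N | Plan's DE | n per arm, plan → DE 1 (one look) | One look, plan → DE 1 | Two looks, plan → DE 1 | Overstatement, √DE − 1 |
|---|---|---|---|---|---|
| 480 | 1.425 | 114.8 → 163.7 | 0.86/1.29 → 0.72/1.08 | 0.90/1.35 → 0.75/1.13 | 19.4% |
| 640 | 1.574 | 138.7 → 218.2 | 0.78/1.17 → 0.62/0.93 | 0.82/1.22 → 0.65/0.97 | 25.4% |
| 800 | 1.722 | 158.4 → 272.8 | 0.73/1.10 → 0.56/0.83 | 0.76/1.14 → 0.58/0.87 | 31.2% |

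The DE = 1 values are the plan's own ICC 0 rows. Power at the printed ICC 0.02 differences is about 97%, 98% and 99% for N = 480, 640 and 800, with one look or two. With one look, 0.78 (SD 2) or 1.17 (SD 3) needs 139.1 effective participants per arm, so a total of 139.1 × 2 × 1.173 / 0.8 ≈ 408.

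**Step 5: if site-by-arm variation was meant.** The plan puts enrolled cell sizes into the design effect and then removes 20% for attrition separately. With cell sizes × 0.8 at N = 640, m̄ = 18.30, DE = 1 + 0.02 × (1.2975 × 18.30 − 1) = 1.455 and n = 218.2 / 1.455 = 150. The detectable differences are 0.75/1.13 (one look) and 0.78/1.18 (two looks), before any small-sample degrees-of-freedom correction. The printed figures do not stand on this reading either.

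**The case against.** The strongest reply is that this concerns a planning assumption and not a slip in calculation. The site-by-arm cell is disclosed, the ICC 0 figures are printed in the same tables, and the rationale labels the 1.17 end conservative. All of that is true. But calling the ICC and SD conservative does not tell the reader that the clustering formula itself does not match the design.

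A second reply is that a design effect of exactly 1 may be too optimistic. PCST is delivered by coaches who each see several participants, and Usual Care has no coach, so correlation within the PCST arm is plausible. As an illustration only, applying 1.574 to the PCST arm alone gives a mean inflation of (1.574 + 1)/2 = 1.287 and about 0.71/1.06; 1.455 gives about 0.69/1.03. The point is fair, and it means that 0.93 makes no allowance for such variation. It does not rescue the printed rows: the plan gives no caseloads, does not link the ICC to coaches or to a varying effect, and has no model term for either.

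Third, the comparison with the 1-point benchmark carries limited weight, because the plan itself warns against applying it to group differences. That stands. It also stands that no decision turns on the error: it is on the safe side, and the amendment history (V1.6) already deals with closing recruitment at the 640th randomisation.

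**Conclusion.** The concern holds. Under individual randomisation within site and the stated primary model, the design effect for the between-arm contrast in change is 1. The ICC 0.02 rows overstate the detectable difference by about 19% (N = 480), 25% (N = 640) and 31% (N = 800), and the power at the printed values is 97% to 99% instead of 90%. At N = 640 the upper planning figure is 0.93 and not 1.17, which moves it from above to below the 1-point individual benchmark, subject to the plan's own caution about that comparison.

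The result takes the plan's attrition, SDs and interim inflation factors as given, and assumes that the ICC describes a site effect common to both arms, as the model has it. N = 640 is not too small on this account, and the estimate, test and stopping bounds are unaffected. The point should be fixed because a stated detectable difference and its power are wrong for this design, but it does not threaten the trial's inference.

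**What to change.** **Main route.** Remove the design effect from Section 10.2.1 and rely on the ICC 0 rows of Tables 10.2 and 10.5. Replace 139 per arm by about 218, and in Section 10.2.1.1 replace 1.17 by about 0.93. This costs text and table edits only.

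**If the sponsor meant the PCST effect to vary between sites.** Say so, recompute rows 4 to 6 of both tables with post-attrition cluster sizes, and reconcile the primary model with that assumption. With one look, the recomputed values for N = 800, 640 and 480 are 0.70/1.05, 0.75/1.13 and 0.83/1.25. With two looks they are 0.73/1.09, 0.78/1.18 and 0.87/1.30. This route costs more because it reopens the primary model. An allowance for coach clustering would likewise need a stated source, caseloads and a matching analysis.

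**Separate clerical point.** In Table 10.2 row 4 (N = 800) the Clinical Center n should read 100, not 80. The printed 0.73/1.10 reproduce with m = 100, whereas m = 80 gives 0.70/1.05. Table 10.5 row 4 already shows 100.

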10.2.1.1. Rationale for the Selected Sample Size

The trial will aim to enroll 640 participants. Based on the minimum detectable differences in changes of BPI Interference scores under a range of assumptions provided in **Table 10.2**, for the primary objective of comparing PCST with Usual Care in Phase 1, this sample size will allow detection of a difference in the change in BPI Interference score of 0.62 if there is no intra-cluster correlation and a standard deviation of change of 2, or 1.17, under the conservative assumptions of an intra-cluster correlation coefficient (ICC) of 0.02 and a standard deviation of change of 3 (which is larger than the SD of change observed in studies of chronic pain in non-ESRD patient populations⁵⁷). Based on a review of the literature, the Initiative on Methods, Measurement, and Pain Assessment in Clinical Trials identified 1 as the minimal clinically important change *for individuals* on the BPI Interference scale.⁵⁷ However, this group also recognized a critical tenet of randomized trials with between group comparisons: "...criteria for clinically important change in individuals cannot be directly applied to the evaluation of clinically important group differences." Determination of the importance of group differences must be established in the broader context of the disease being treated, the currently available treatments, and the overall risk-benefit evaluation of the treatment. Our proposed sample size will allow us to detect a between-group difference *as small as* the ranges listed above. We hypothesize that the actual observed difference will be larger because we are testing an adaptation of an evidence-based intervention that has had moderate effect sizes in other populations and settings.²⁷⁻²⁹

10.2.2. Statistical Analyses

General Approach. The following descriptive statistics will be used: number of observations, mean, standard deviation, median, minimum and maximum for continuous variables; frequencies and proportions for categorical variables; number of events and rates for count variables. Results will be reported in accordance with the extended CONSORT guidelines for pragmatic clinical trials⁶¹ using two-sided statistical tests and confidences intervals. For all analyses, the overall level of significance will be set at 0.05. Methods for multiple comparisons such as Bonferroni, false discovery, or others, will be implemented to maintain the overall 0.05 level of significance. All analyses will be adjusted for site and the presence or absence of opioid use using the criteria provided in **Section 5.3**. All analyses will be performed using SAS v9.4 (SAS Institute, Cary, NC) or the latest version of R (currently 3.6.1; <https://cran.r-project.org/>).

Baseline Descriptive Statistics. Randomization adequacy will be assessed by comparing the distributions of baseline demographic and clinical characteristics between the PCST and Usual Care groups. Comparability for continuous variables will be examined graphically and by summary statistics: mean, standard deviation, median, minimum, and maximum for continuous variables, and frequency and proportion for categorical variables. If statistically and/or clinically meaningful differences are found in baseline characteristics (i.e., baseline characteristics are not balanced between the PCST and Usual Care groups), sensitivity analyses will be conducted with covariate adjustment.

